## 2.3. Benefit/risk assessment

More detailed information about the known and expected benefits and risks and reasonably expected adverse events (AEs) of paroxetine may be found in the [GSK Seroxat SmPC 2022](#).

### 2.3.1. Risk assessment

Paroxetine has a well-characterized safety profile supported by over 30 years on the market across a number of indications, and a large cumulative post-marketing exposure. Information about the known and potential risks and reasonably expected AEs may be

**CONFIDENTIAL**

Protocol and Version 2.0 (Final)

found in the [GSK Seroxat SmPC 2022](#). Potential risks of clinical significance for this particular study are summarised below.

## CONFIDENTIAL

## Protocol and Version 2.0 (Final)

| Potential Risk of Clinical Significance                       | Summary of Data/Rationale for Risk   | Mitigation Strategy   |
|---|--|---|
| Study Intervention(s) [Paroxetine]                            |  |   |
| Serotonin Syndrome/Neuroleptic malignant syndrome like events | 
Serotonin syndrome has been reported very rarely in patients treated with paroxetine.
 
Paroxetine belongs to a class of drugs known as SSRIs whose antidepressant activity results from their ability to selectively increase synaptic levels of serotonin in the brain. Overstimulation of the serotonergic system can lead to serotonin syndrome.
 
Symptoms of serotonin syndrome may include any or all of the following (note that other symptoms may be exhibited): agitation, confusion, diaphoresis, hallucinations, hyperreflexia, myoclonus, shivering, tachycardia and tremor. Symptoms may worsen with continued therapy and can be life threatening.
 
Serotonin syndrome may occur at any time during treatment with paroxetine. It may be more likely to occur if paroxetine is co-administered with other serotonergic drugs. Of note, although most likely to occur through the combined use of various serotonergic drugs, GSK has received rare post-marketing reports of the development of serotonin syndrome in patients receiving paroxetine in the absence of other serotonergic co-medications
 | 
Participants are forbidden to receive other serotonergic medications during the study (see Section 5.2, Exclusion criteria)
 
Participants should be alerted to the potential symptoms of serotonin syndrome.
 
If a participant experiences serotonin syndrome/neuroleptic malignant syndrome like symptoms during the study, paroxetine should be discontinued and the participant withdrawn from the study.
 |

|  |   |  |
|--|---|--|
| Bleeding disorders, predominantly of the skin and mucous membranes | 
Abnormal bleeding, predominantly of the skin and mucous membranes has been reported uncommonly in patients receiving paroxetine. Gastrointestinal bleeding is estimated to be very rare. Abnormal bleeding may occur at any time during treatment with paroxetine.
 
SSRIs are antagonists of the serotonin transporter system which can lead to a lower concentration of serotonin in platelets. Serotonin mediates vasoconstriction, platelet aggregation and platelet activation following injury, and because platelets cannot synthesize serotonin, treatment with SSRIs can lead to a reduction of platelet serotonin and therefore impair haemostasis.
 
Symptoms and outcomes of blood loss can vary depending on a number of factors such as the volume of blood loss, rate of loss and cause of the loss. Symptoms of more severe blood loss (indicating hypovolaemic shock) may include pale skin, rapid breathing, sweating, weakness, no or decreased urine output, confusion, clammy skin, unconsciousness and death. Depending on the severity of the blood loss immediate medical treatment may be required and may necessitate blood transfusion in extreme cases.
 
Patients more at risk from paroxetine induced bleeding related adverse events will be those who are concomitantly using medications that may increase the risk for bleeding such as nonsteroidal anti-inflammatory drugs (NSAIDs), anticoagulants, antiplatelet medications or corticosteroids. Additionally, those patients with a known tendency for bleeding or those with predisposing conditions such as previous history of gastrointestinal bleeding, elderly patients or those with history of peptic
 | 
As per exclusion criteria (refer to Section 5.2), subjects cannot participate in the study if they have a history of/or concurrent abnormal coagulation parameters, a bleeding disorder or conditions which may pre-dispose the subject to bleeding.
 
Participants are forbidden to receive concomitant medications during the study which might increase the risk for bleeding events (anticoagulants (e.g. warfarin), non-steroidal anti-inflammatory drugs, acetylsalicylic acid or Cox 2 inhibitors (refer to section 5.2, Exclusion Criteria)
 
Participants should be made aware of the symptoms of blood loss.
 
If the participant experience blood loss during the study, treatment with paroxetine should be discontinued and the participant withdrawn from the study.
 |
|--|---|--|

**CONFIDENTIAL**

Protocol and Version 2.0 (Final)

|  |  |  |
|--|--|--|
|  | ulcers, cirrhosis of the liver or liver failure will be at increased risk. |  |
|--|--|--|

|           |   |   |
|-----------|---|---|
| Akathisia | 
Rarely, the use of paroxetine or other SSRIs has been associated with the development of akathisia, which is characterised by an inner sense of restlessness and psychomotor agitation such as an inability to sit or stand still usually associated with subjective distress. This is most likely to occur within the first few weeks of treatment.
 
The mechanism for akathisia is not completely understood but it is postulated to be related to a decrease in dopaminergic neurotransmission and it has been suggested that SSRIs induce akathisia (and parkinsonism) by indirectly stimulating serotonin (5-HT)2A receptors, which results in inhibition of dopamine release.
 
Risk factors for the development of akathisia in patients taking paroxetine may include the use of multiple medications that can cause akathisia (such as neuroleptics, other SSRIs, antiemetics), a recently increased or high dose of SSRI, previous development of akathisia, previous exposure to akathisia inducing medications, baseline psychiatric disorders such as anxiety, agitation or panic, brain trauma and female sex. There is also suggestion that akathisia can occur spontaneously in patients with Parkinson's Disease
 | 
Study participants must be healthy as determined by a responsible physician. Participants with a previous history of depression or other mood disorders will be excluded from study participation (refer to sections 5.1 and 5.2, (Inclusion and Exclusion Criteria respectively).
 
Participants are prohibited from receiving concomitant medications during the study including neuroleptic drugs or other SSRIs (refer to section 5.2, Exclusion Criteria)
 
Dose increases of paroxetine (20 mg increments) will be conducted under supervision in the clinic.
 
Participants should be made aware of the symptoms of akathisia.
 
If a participant experiences symptoms of akathisia during the study, discontinuation of paroxetine should be considered.
 |
|-----------|---|---|

**CONFIDENTIAL****Protocol and Version 2.0 (Final)**

|  |   |  |
|--|---|--|
| Symptoms seen on discontinuation of paroxetine | 
In clinical trials in adults, adverse events seen on treatment discontinuation occurred in 30% of patients treated with paroxetine compared to 20% of patients treated with placebo.
 
Common adverse events which can occur following discontinuation of treatment with paroxetine include: dizziness, sensory disturbances, sleep disturbances, anxiety and headache. Adverse events including agitation, nausea, tremor, confusion, sweating and diarrhoea have also been reported uncommonly after discontinuing paroxetine treatment.
 
Discontinuation type symptoms are most likely to occur on abrupt discontinuation of paroxetine but have also been seen during the dose taper phase of treatment. Generally, these symptoms are self-limiting and usually resolve within 2 weeks, though in some individuals they may be prolonged (2-3 months or more).
 
It is recommended that paroxetine should be gradually tapered when discontinuing treatment over a period of several weeks or months.
 | 
After the study dosing period (up to 60 mg daily) participants will be undergoing gradual tapering of their paroxetine dose in decrements of 20 mg over a total tapering period of ten days. Refer to section 1.2, Schema.
 
Participants should be made aware of the type of symptoms which might occur during the tapering phase.
 
Withdrawal symptoms generally tend to be self-limiting. However, based on PI's clinical assessment of withdrawal symptoms during the tapering phase of 20 mg OD to no paroxetine, an additional 5 days of 10 mg OD paroxetine may be provided.
 
In addition, withdrawal symptoms may be treated, at the PI's discretion, as clinically indicated.
 |
|--|---|--|

**CONFIDENTIAL****Protocol and Version 2.0 (Final)**

|                              |  |  |
|------------------------------|--|--|
| Suicidality/suicide ideation | 
Young adults, especially those with major depressive disorder, may be at increased risk for suicidal behaviour during treatment with paroxetine.
 
An analysis of placebo-controlled trials of adults with psychiatric disorders showed a higher frequency of suicidal behaviour in young adults (prospectively defined as aged 18 to 24 years) treated with paroxetine compared with placebo (17/776 [2.19%] versus 5/542 [0.92%]), although this difference was not statistically significant. In the older age groups (aged 25 to 64 years and <math>\geq 65</math> years), no such increase was observed.
 
In adults with MDD (all ages), there was a statistically significant increase in the frequency of suicidal behaviour in patients treated with paroxetine compared with placebo (11/3455 [0.32%] versus 1/1978 [0.05%]; all of the events were suicide attempts). However, the majority of these attempts for paroxetine (8 of 11) were in younger adults aged 18 to 30 years. These major depressive disorder data suggest that the higher frequency observed in the younger adult population across psychiatric disorders may extend beyond the age of 24.
 | 
A Colombia Suicide Severity Rating Scale (C-SSRS) will be taken at screening. Participants with a history of suicidal attempt/ideation or those having undergone previous assessment for suicide ideation will be excluded from the study along with participants with a history of depression or a pre-diagnosed mood disorder (refer to Section 5.2, Exclusion Criteria).
 
Participants will be monitored for suicidal ideation as part of regular AE monitoring either in person (during study Visits) or via a video call (when dosing at home). In addition to the C-SSRS taken at screening, repeat C-SSRS may be administered at the PI's discretion, as clinically indicated.
 |
|------------------------------|--|--|

**CONFIDENTIAL****Protocol and Version 2.0 (Final)**

|                    |  |  |
|--------------------|--|--|
| Pregnancy Outcomes | 
Congenital malformations: Epidemiological studies of pregnancy outcomes following maternal exposure to antidepressants in the first trimester have reported an increase in the risk of congenital malformations, particularly cardiovascular (e.g. ventricular and atrial septal defects), associated with the use of paroxetine. The data suggest that the risk of having an infant with a cardiovascular defect following maternal paroxetine exposure is approximately 1/50, compared with an expected rate for such defects of approximately 1/100 infants in the general population.
 | 
A female participant is only eligible to participate in the study if she is of nonchildbearing potential or of childbearing potential but having agreed to use one of the accepted methods of contraception as detailed in section 8.1.
 
Pregnant females as determined by positive serum <math>\beta</math>-HCG test at screening or serum/ urine <math>\beta</math>-HCG prior to dosing will be excluded from the study.
 
If a female participant becomes pregnant during the study, paroxetine treatment should be discontinued and the participant withdrawn from study participation. (Refer to section 8.4.5. Follow-up information on the pregnancy will be collected and monitored as per company pharmacovigilance procedures.
 |
|--------------------|--|--|

**2.3.2. Benefit assessment**

It is not anticipated that there will be any direct benefit for participants participating in this study. An indirect benefit is that the information obtained in this study will support the continued understanding of the safety profile of paroxetine and support appropriate prescribing in patients with underlying cardiac risks.

**2.3.3. Overall benefit-risk conclusion**

Considering the measures taken to minimize the risk to participants participating in this study, the potential risks are justified by the potential benefits related to the continued understanding of the safety profile of paroxetine.

### 3. OBJECTIVES, ENDPOINTS AND ESTIMANDS

| Objectives  | Endpoints  |
|---|--|
| Primary  |  |
| 
 
To evaluate the potential effect of paroxetine on QTc interval following oral doses of 20, 40, and 60 mg once daily in healthy adults
 
 | 
 
Change in QTc from baseline (<math>\Delta QTc</math>).
 
   |
| Secondary  |  |
| 
 
To assess the safety and tolerability of paroxetine doses of 20, 40, and 60 mg once daily in healthy adults
 
                           | 
 
Changes in vital signs (blood pressure, heart rate and oral body temperature) from baseline
 
Occurrence of adverse events (AEs), serious adverse events (SAEs), haematological and clinical laboratory tests*, vital signs, and physical examination
 
 |

\* Laboratory tests will include full blood count, INR, PT, PTT renal ( $Na^+$ ,  $K^+$ , Cl, creatinine) and hepatic (AST, ALT) markers.

#### Primary estimand

The primary question of interest is: Is there a clinically significant, and clinically relevant cardiac effect of paroxetine at the maximum recommended therapeutic dose, as measured by a change in QTc from 12-lead ECG?

The estimand is described by the following attributes:

- Population: Healthy participants of age 18 to 65 years
- Treatment condition: Dose up titration of paroxetine doses of 20, 40 and 60 mg.
- Variable/endpoint: Change in QTc from baseline ( $\Delta QTc$ )
- Summary measure: The upper limit of the 90% confidence interval (CI) of model-predicted  $\Delta QTc$  at the geometric mean steady-state  $C_{max}$  of the 60 mg paroxetine dose.
- Intercurrent events:
  - Treatment discontinuation due to any reason - While on-treatment strategy will be applied to address this intercurrent event.
  - Any events affect the drug absorption (1 hour) – Treatment Policy strategy will be applied to address this intercurrent event.
- Rationale for estimand:
  - Interest lies in establishing the relationship between  $\Delta QTc$  and paroxetine concentrations ( $C_{max}$ ) while the participant is exposed to paroxetine as planned, i.e., prior to the discontinuation of the treatment.

b. Interest lies in the overall relationship between the  $\Delta QTc$  and paroxetine concentrations, not with dose - therefore even though the concentration for a dose is affected, the data are still relevant.

If this summary measure is  $\geq 10$  msec, additional summary measure may be generated at the geometric mean  $C_{max}$  of the 40 mg dose. Additionally, another estimand might need to be evaluated.

Refer to [Section 9.3.2](#) for more details.

### Secondary estimands

Secondary estimands address all other safety and tolerability findings.

The estimand is described by the following attributes:

- Population: Healthy participants of age 18 to 65 years
- Treatment condition: Dose up and down titration of paroxetine doses of 20, 40 and 60 mg
- Variable/endpoint:
  - Occurrence of adverse events (AEs) and serious adverse events (SAEs)
  - Changes in vital signs (blood pressure, heart rate and oral body temperature) from baseline
  - Changes in haematological and clinical laboratory tests from baseline
- Summary measure: Proportions for AEs and SAEs and means of the change from baselines for vital signs, haematological, and clinical laboratory across all dose levels.
- Intercurrent events: Study treatment discontinuation due to any reason – treatment policy strategy will be applied for this intercurrent event.
- Rationale for Estimand: Safety data will be monitored throughout the study after the start of treatment. There is interest in evaluating and reporting safety events regardless of whether participants discontinued treatment.

## 4. STUDY DESIGN

### 4.1. Overall design

This is an open-label, single arm, dose-escalating concentration QT study to investigate the cardiac effects, safety and tolerability of paroxetine in healthy adult participants.

At least 36 participants with no history of cardiac abnormalities or mood disorders will be enrolled. All eligible participants will receive paroxetine titrated to a dose of 60 mg once daily at increments of 20 mg per week.

All participants will attend a study site visit at Screening (Visit 1: -28 to -31 days), baseline (pre-dose) assessments and first paroxetine administration of 20 mg once daily (Visit 2: Day 1), serial ECG and paroxetine concentration measurements (Visit 3, Day 7)

and dose escalation to 40 mg once daily (Visit 3: Day 8), serial ECG and paroxetine concentration measurements at the 40 mg dose (Visit 4, Day 14) and dose escalation to 60 mg once daily (Visit 4: Day 15), serial ECG and paroxetine concentration measurements (Visit 5, Day 21) and the Exit visit (Visit 6, up to 14 days after last 20 mg dose). Tapering from 60 to 40 mg once daily, 40 to 20 mg once daily, and 20 mg once daily to no dose will occur at home. Unplanned visits (if needed) will be scheduled for participants who needs to visit to clinic due to AEs during home dosing or required to start intermediate tapering dose of 10 mg to be started (for both clinic and home dosing) during the treatment period.

During home dosing participants will be interviewed remotely via video-call to confirm dosing compliance and have daily follow-ups. The study design schema is presented in Figure 1. The intervals between study visits are presented in Table 2.

### **Intervention Groups and Duration:**

All participants will receive active treatment with paroxetine tablets once daily with titration steps every week over a maximum treatment period of 3 weeks. This is followed by tapering over the subsequent period of 10 days:

- Days 1 -7: 20 mg once daily
- Days 8 -14: 40 mg once daily
- Days 15- 21: 60 mg once daily
- Days 22-26: 40 mg once daily
- Days 27-31: 20 mg once daily. If participants are not able to withdraw from 20 mg once daily directly due to withdrawal effects, an additional tapering dose step of 10 mg once daily may be given for 5 days. Unplanned visits (if needed) will be scheduled for participants who need to visit to clinic due to AEs during home dosing or required to start intermediate tapering dose of 10 mg to be started (for both clinic and home dosing) during the treatment period.
- Day 32 (or 37) onwards: complete stop of paroxetine

### **4.2. Scientific rationale for study design**

This is a single arm, open label, dose escalating concentration QT study to investigate the cardiac effects, safety and tolerability of paroxetine in healthy adult participants.

Participants recruited in this study will not be allowed to take other co-administered medication other than paracetamol and will be managed according to routine medical care where relevant. In vitro studies have shown that paroxetine can block hERG channels, which in turn can cause QT prolongation. However, clinical reports evaluating an association between paroxetine exposure and QTc prolongation are limited and vary in their conclusions. Based on the available data from published literature, GSK and EudraVigilance safety databases and clinical studies, it has been concluded that there is some basis for suspicion of an association of QT prolongation with paroxetine, but current evidence does not confirm a causal relationship (GSK document 2021N481496). Following a careful assessment of the suitable approaches to characterise the magnitude

of a potential QT prolonging effect, a concentration-QT study was determined to be appropriate to further investigate the potential risk.

#### **4.2.1. Participant input into design**

No participants' input in the design has been considered for this study.

#### **4.3. Justification for dose**

For adults, it is recommended that paroxetine is administered once daily in the study site in the morning with food. The tablets should be swallowed rather than chewed. The 20 mg tablets have functional break lines to allow for breaking the tablets in half to yield 10 mg doses if needed. As per the Paroxetine label (GDS, 2023), the recommended maintenance dose in adults is 20 mg. The current study will employ a titration design to limit the probability of side-effects occurring, with escalating doses up to 60 mg paroxetine q.d., which corresponds to the maximum recommended therapeutic paroxetine dose.

In this study, all participants will receive active treatment with paroxetine tablets once daily with titration/escalation steps every week over a maximum treatment period of 3 weeks. This is followed by tapering over the period of 10 days as detailed in [Section 4.1](#). If intolerable withdrawal symptoms occur during down titration of paroxetine from 20 mg once daily to no dose, then an intermediate tapering step of 10 mg once daily for an additional 5 days will be allowed. In this case the final follow-up visit will remain up to 14 days after the last 20 mg dose. An unplanned visit (if needed) will be scheduled for participants for an intermediate tapering dose of 10 mg to be started (for both clinic and home dosing) during the treatment period or for those participants who needs to visit to clinical due to AEs after dosing was performed at home.

#### **4.4. End-of-study definition**

A participant is considered to have completed the study if they have completed all phases of the study, including the last visit for any protocol-related activity (last participant, last visit) as shown in the SoA ([Section 1.3](#)) are completed.

The end of the study is defined as the last visit of the last participants in the study.

### **5. STUDY POPULATION**

Prospective approval of protocol deviations to recruitment and enrolment criteria, also known as protocol waivers or exemptions, are not permitted.

## 5.1. Inclusion criteria

Participants are eligible to be included in the study only if all of the following criteria apply:

1. Male or female 18 to 65 years, at the time of signing the informed consent form.
2. Healthy as determined by an experienced physician, based on a medical evaluation including medical history, physical examination, laboratory tests and cardiac monitoring. A participant with a clinical abnormality or laboratory parameters outside the reference range for the population being studied may be included only if the Investigator believes that the finding is unlikely to introduce additional risk factors and will not interfere with the study procedures.
3. A female participant is eligible to participate if she is of:
  - a. Nonchildbearing potential defined as premenopausal females with a documented tubal ligation or hysterectomy; or postmenopausal defined as 12 months of spontaneous amenorrhea [in questionable cases a blood sample with simultaneous follicle stimulating hormone (FSH)  $> 40\text{IU/L}$  and oestradiol  $< 40\text{ pg/ml}$  ( $< 147\text{ pmol/L}$ ) is confirmatory]. Females on hormone replacement therapy (HRT) and whose menopausal status is in doubt will be required to use one of the contraception methods (oral contraceptives, condom with spermicide, etc.) if they wish to continue their HRT during the study. Otherwise, they must discontinue HRT to allow confirmation of postmenopausal status prior to study enrolment. For most forms of HRT, at least 2-4 weeks will elapse between the cessation of therapy and the blood draw; this interval depends on the type and dosage of HRT. Following confirmation of their postmenopausal status, they can resume use of HRT during the study without use of a contraceptive method.
  - b. Child-bearing potential and agrees to use one of the contraception methods listed in Appendix 4 for at least for 2 months before screening, up to the final follow up visit, to sufficiently minimize the risk of pregnancy.
4. AST, ALT, alkaline phosphatase and bilirubin  $\leq 1.5\times\text{ULN}$  (isolated bilirubin  $>1.5\times\text{ULN}$  is acceptable if bilirubin is fractionated and direct bilirubin  $<35\%$ ).
5. Body weight  $\geq 45\text{ kg}$  and BMI within the range 18 to  $29.5\text{ kg/m}^2$  (inclusive).
6. No significant abnormality on 12-lead ECG at Screening in supine position, including the following specific requirements:
  - a. Heart rate  $\geq 40$  beats per minute
  - b. PR interval  $\leq 220\text{msec}^*$
  - c. Q waves  $< 50\text{msec}^*$
  - d. QRS interval to be  $\geq 60\text{msec}$  and  $< 120\text{msec}^*$
  - e. The waveforms must enable the QT interval to be clearly defined
  - f. QTcF interval must be  $< 450\text{msec}$  (machine or manual reading).

\*For PR, QRS and QTcF interval, and Q wave, the mean of triplicate ECGs will be used.
7. Capable of giving written informed consent and a signed and dated written informed consent is obtained, which includes compliance with the requirements and restrictions listed in the consent form.

8. Non-smokers (never smoked or not smoking for >6 months with <10 pack years history (Pack years = (cigarettes per day smoked/20) x number of years smoked) or light smokers (less than 5 cigarettes per day).

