#### 10.4.1.2. Woman of Nonchildbearing Potential (WONCBP)

Women in the following categories are considered WONCBP:

- Premenarchal: Tanner stage 1 (prepubertal)

Permanently sterile due to one of the following procedures:

- a. Documented hysterectomy
- b. Documented bilateral salpingectomy
- c. Documented bilateral oophorectomy

For permanently sterile individuals due to an alternate medical cause other than the above, (e.g., Mullerian agenesis, androgen insensitivity, gonadal dysgenesis), Investigator discretion should be applied to determining study entry. If reproductive status is questionable, additional evaluation should be considered.

Note: Documentation can come from the site personnel's review of the participant's medical records, medical examination, or medical history interview.

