#### **10.4.2. Contraception guidance**

Patients of childbearing potential and participants with partners of childbearing potential must agree to practice highly effective contraception plus one barrier method during their participation in the study and after the last dose of paroxetine or longer if determined by country requirement. Female patients must use contraception for at least 2 months before screening, up to the final follow up visit. Patients must refrain from donating sperm during their participation in the study and following last dose.

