##### Highly effective forms of contraception

Highly effective forms of contraception include one or more of the following:

- Male partner who is sterile (medically effective vasectomy) prior to the female participant's entry into the study and is the sole sexual partner for the female participant
- Combined (estrogen and progestogen-containing) hormonal contraception associated with inhibition of ovulation (oral, intravaginal or transdermal)
- Progestogen-only hormonal contraception associated with inhibition of ovulation (oral, intravaginal or transdermal)
- An intrauterine device
- Bilateral tubal occlusion

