##### Childbearing potential

Childbearing potential is defined as one of:

- <50 years of age unless amenorrheic for at least 12 months following the cessation of exogenous hormonal treatments, and have serum follicle-stimulating hormone and luteinizing hormone levels in the postmenopausal range for the institution.
- ≥50 years of age and has had menses within 12 months following cessation of all exogenous hormonal treatments.
- Not irreversibly surgically sterilized by hysterectomy, bilateral oophorectomy, or bilateral salpingectomy.

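### Section 5.1 and Appendix 4 disagree on tubal ligation and on one versus two contraceptive methods, and the medication rules make no allowance for the hormonal methods that Appendix 4 lists

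*Protocol*

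**What the plan says.** All references are to the Protocol.

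**Sterility.** Section 5.1 (3a) gives "Nonchildbearing potential defined as premenopausal females with a documented tubal ligation or hysterectomy". Section 10.4.1.2 introduces a closed surgical list with "Permanently sterile due to one of the following procedures"; it contains hysterectomy, bilateral salpingectomy and bilateral oophorectomy. Section 10.4.2 repeats that list in defining childbearing potential: "Not irreversibly surgically sterilized by hysterectomy, bilateral oophorectomy, or bilateral salpingectomy". Its list of highly effective contraception includes "Bilateral tubal occlusion".

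**Number of methods.** Section 5.1 (3b) asks for one of the Appendix 4 methods. The 3a sentence on HRT users of doubtful menopausal status also asks for one, gives oral contraceptives and condom with spermicide as examples, and does not cite Appendix 4. Section 2.3.1 asks for one accepted method and sends the reader to Section 8.1. Section 10.4.2 says that participants "must agree to practice highly effective contraception plus one barrier method during their participation in the study".

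**Medication.** Section 4.2 allows only paracetamol. Section 6.9 allows paracetamol and HRT and prohibits everything else. Exclusion 19, copied in Table 9, names only paracetamol. Section 10.4.2 nevertheless lists "Combined (estrogen and progestogen-containing) hormonal contraception associated with inhibition of ovulation" and "Progestogen-only hormonal contraception associated with inhibition of ovulation" among its highly effective methods.

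**Precedence.** No text says which section governs, and Section 5 permits no waivers.

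**The concern.** Section 2.3.1 puts the risk of a cardiovascular defect after maternal exposure at about 1/50, against about 1/100 in the general population. It gives contraception as one of its mitigations. The participants are healthy volunteers, and Section 2.3.2 expects no direct benefit for them. Site staff should therefore find one answer to three questions: who needs contraception, how many methods she needs, and which methods she may use. As written, the answer depends on the page consulted.

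The error can go either way. A woman of childbearing or doubtful status could be accepted on a single barrier method. A woman on the pill, which 3a names and which 10.4.2 accepts as highly effective, could be refused under the medication rules.

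**Working it through.** The plan gives no figure to reproduce. The check sets the texts side by side and adds simple counts.

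| Question | Section 5.1, 2.3.1 or medication rules | Appendix 4 |
|---|---|---|
| Premenopausal, tubal ligation only | Non-childbearing (3a) | Not in the sterility lists (10.4.1.2, 10.4.2); occlusion is a contraceptive method |
| Methods required | 1 (3b, 2.3.1, 3a HRT sentence) | 1 highly effective + 1 barrier = 2 (10.4.2) |
| Hormonal contraceptives | Not among permitted medication (4.2, 6.9, intent of Exclusion 19) | Two listed as highly effective (10.4.2) |
| HRT | Permitted in 6.9; not in 4.2 or Exclusion 19 | Conditions in 10.4.1.2 |

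**Size of the tubal ligation conflict.** Under 3a she needs no contraception. Under 10.4.2 she already has a highly effective method and must add one barrier. She is eligible under both, so the difference is one barrier method.

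- Dosing days (Section 4.1): 7 + 7 + 7 + 5 + 5 = 31, or 31 + 5 = 36 with the 10 mg step.
- Final visit (Table 1, 9 to 14 days after the last dose): Day 31 + 9 = Day 40 to Day 31 + 14 = Day 45. With the 10 mg step, Section 4.3 keeps the visit within 14 days of the last 20 mg dose, so Day 45 remains the latest.
- Screening falls on Day -31 to Day -28, and there is no Day 0. Shortest span: 28 + 40 = 68 days. Longest: 31 + 45 = 76 days. This counts participation from screening.

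**Can one and two methods be reconciled?** For 3b, partly. It cites Appendix 4, so a reader may apply both and require two methods. Its literal wording still admits one, and Appendix 4 lists barrier methods too. For the other two places, no. The 3a HRT sentence offers condom with spermicide without citing Appendix 4, and Section 8.1, to which 2.3.1 refers, covers demographics and medical history and lists no methods.

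**Hormonal methods.** Section 10.4.2 lists five highly effective methods: a vasectomised sole partner, combined hormonal, progestogen-only hormonal, an intrauterine device and tubal occlusion. Two are hormonal, so 5 - 2 = 3 remain under the medication rules, assuming an intrauterine device without hormone.

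**Exclusion 19.** The list excludes anyone to whom an item applies, and item 19 is phrased as the absence of medication use. Taken literally it would exclude people who take nothing. Its intent is plainly the opposite, but Sections 4.2 and 6.9 carry the point better.

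**HRT timing.** Section 6.9 permits HRT throughout the study and then, in the same sentence, only during screening. Both cannot hold.

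**The case against.** The strongest reply has four parts.

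1. *A woman using both kinds of method satisfies every section, and Exclusion 24 removes anyone unwilling to follow the procedures.* This is true and softens the conflict in 3b. It does not reach the 3a HRT sentence or Section 2.3.1.

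2. *The HRT rules do not conflict.* A reader might infer a flat contradiction, because 3a lets a woman of doubtful status stay on HRT with contraception while 10.4.1.2 says she must stop. The documents do not support that reading firmly. The 10.4.1.2 sentence stands under the definition of a postmenopausal woman, and 3a has nearly the same sentence as its alternative branch. It can be read as the condition for being classed postmenopausal. The under-50 bullet in 10.4.2 fits this reading: she counts as of childbearing potential "unless amenorrheic for at least 12 months following the cessation of exogenous hormonal treatments", which a woman still taking HRT cannot meet. What stands is an ambiguity.

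3. *The bar on hormonal contraceptives is only a missing exception.* Section 3a and Appendix 4 show that they were meant to be allowed, and the specific drug list in Exclusion 17 does not name them. That is probably right about intent. The prohibition in 6.9 is nonetheless unqualified, and waivers are not available.

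4. *Contraception is not the only safeguard.* Correct. Section 2.3.1 also lists exclusion on a positive hCG test and discontinuation on pregnancy, and Section 8.3.5 requires a negative test before dosing in women of childbearing potential.

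**Conclusion.** The point holds as a minor safety-consistency correction. Two rules conflict between Section 5.1 and Appendix 4: the status of tubal ligation, and one method against two. Separately, the medication rules do not permit 2 of the 5 highly effective methods in 10.4.2, and they treat HRT inconsistently.

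The effect is small. For a woman with tubal ligation it is one added barrier for 68 to 76 days, 31 or 36 of them dosing days. The documents do not say how many women are concerned; the Synopsis caps enrolment at 40, men included.

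Three stronger inferences are not supported:

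- *That women with tubal ligation would go untested for pregnancy.* Section 8.3.5 applies to women of childbearing potential, a class that under Appendix 4 includes them. Loss of testing is not shown.
- *That no compliant method is available.* Three non-hormonal highly effective methods remain.
- *That the QT result is at risk.* The conflicts concern eligibility and fetal risk and do not enter the concentration-QT model.

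**What to change.** (a) In 3a, remove tubal ligation and refer to Section 10.4.1.2 for surgical sterility. Tubal occlusion stays a highly effective method in 10.4.2.

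(b) In 3b, Section 2.3.1 and the 3a HRT sentence, require a highly effective method plus one barrier method as in Section 10.4.2, during participation up to the final follow-up visit. Keep the 2-month pre-screening requirement in 3b. In 2.3.1 this replaces the pointer to Section 8.1; in 3a it replaces the bracketed examples.

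(c) In 10.4.1.2, state that a woman on HRT of doubtful menopausal status who does not stop HRT for confirmation is treated as of childbearing potential and follows 10.4.2.

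(d) In Sections 4.2 and 6.9, Exclusion 19 and its copy in Table 9, permit HRT and the hormonal contraceptives listed in 10.4.2. Reword Exclusion 19 and the copy to begin with current use of any medication other than those permitted, which removes the double negative. In 6.9, delete the trailing words that confine use to screening.

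**Cost.** Protocol wording, with the IRB/IEC approval and reconsent that an eligibility amendment may need. There may be a few more screen failures among women unwilling to add a barrier; permitting hormonal methods works the other way. No added visits or tests.
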